8.7.1.3 Extent of Study Exposure and Follow-up

The duration of study will be summarized by treatment group using descriptive statistics (number of patients, mean, median, standard deviation, minimum, maximum).

Duration on study (months) = (earlier of study exit date and death date – randomization date + 1) / 30.4375

In addition, an alternative method for determining duration of follow-up will be performed using the reverse Kaplan-Meier method for the mITT population. The censored values for OS will be reversed so that 1's will be 0's and 0's will be 1's. The median follow-up time will be derived from the Kaplan-Meier method using the OS values of overall survival and the reversed censoring values.

8.7.1.4 Best Available Care Post-Progression

The number and percentage of patients who received each post-progression treatment (systemic treatments will be presented by preferred terms) will be summarized by treatment group.

8.7.2 Adverse Events

The investigator's verbatim term of each AE will be mapped to system organ class and preferred term using the MedDRA Version 14.0 dictionary.

Adverse events will be summarized by system organ class and preferred term; a patient will only be counted once per system organ class and once per preferred term within a treatment. Patient counts and percentages and event counts will be presented for each treatment group for the following summaries:

1. Overall summary of TEAEs
2. All TEAEs (also presented by preferred term only in descending order).
3. All TEAEs with CTCAE grade ≥ 3 (also presented by preferred term only in descending order).
4. All TEAEs considered related to sorafenib.
5. All TEAEs considered related to device (ADE).
6. All CTCAE grade ≥ 3 TEAEs considered related to device.
7. All TEAEs related to angiographic procedure.
8. All TEAEs with fatal outcome.
9. All treatment emergent serious adverse events (SAE).
10. All treatment emergent serious adverse device events (SADE)
11. All TEAEs leading to sorafenib discontinuation
12. All TEAEs of special interest (presented by AESI category and preferred term)
13. All TEAEs of special interest with CTCAE grade ≥ 3 (presented by AESI category and preferred term)

Event rate (per 100 patient years) will also be presented by treatment group for each of the above TEAE categories. For each category, the event rate is defined as the number of patients with TEAEs in that category divided by the total duration of patients at risk for TEAEs and then multiplied by 365.25×100 to present in terms of per 100 patient years.

For the summary of TEAEs by CTCAE grade, if a patient has multiple events occurring in the same body system or same preferred term, then the event with the highest CTCAE grade will be counted. For TEAEs by relationship to study device, if a patient has multiple events occurring in the same body system or same preferred term, the event with the highest association to study device will be summarized (unknown is considered a higher association to study device than not related, but less of a relationship than possibly, probably, and definitely). Adverse events related to sorafenib, device and angiographic procedure are defined as a subset of AEs with a relationship of either possibly, probably, definitely, or unknown.

No statistical inference between the treatments will be performed on AEs.

Listings will be presented by patient for all AEs as well as for SAEs including SADE, AEs with fatal outcome, and AEs leading to discontinuation of sorafenib.

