9.2.15 STUDY TREATMENTS

9.2.15.1 THERASPHERE

TheraSphere will be administered to the diseased lobes present at randomization, before initiation of the SOC sorafenib treatment. Patients with unilobar disease will receive treatment of the diseased lobe. Patients with bilobar disease will have the second procedure visit such that the second administration occurs within Weeks 5-8 following randomization.

SOC Sorafenib will be prescribed in accordance with the sorafenib package insert. To minimize the risk of additive or synergistic adverse events, sorafenib and TheraSphere should not be administered concurrently. SOC sorafenib treatment will be initiated at least two (2) weeks after the administration of TheraSphere is completed. Generally, patients should initiate SOC sorafenib between 2 and 6 weeks after TheraSphere has been administered to all disease present at randomization.

Safety Risks will be minimized by treating all liver tumors present at randomization with TheraSphere followed by an interval of at least 2 weeks prior to initiating sorafenib therapy to allow decay of the radioactive microspheres and recovery from the expected transient adverse effects (fatigue, abdominal pain, nausea/vomiting) associated with TheraSphere administration. Ideally, SOC sorafenib should be started no later than 6 weeks following TheraSphere treatment.

During follow-up, for patients in the Treatment group who have demonstrated hepatic progression with hepatic lesions amenable to TheraSphere, re-treatment with TheraSphere is allowed. Sorafenib will be discontinued seven (7) days prior to TheraSphere treatment (equivalent to approximately five to seven half-lives) through 2 weeks after TheraSphere treatment to permit radioactive decay and patient recovery from transient side effects.

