10.2.4 SAFETY ANALYSES

The safety analyses will be performed on the SA population.

All treatment emergent adverse events (TEAEs), defined as events which were not present at baseline or worsened in severity following the start of treatment, will be reported according to NCI Criteria. The incidence of TEAEs will be summarized according to MedDRA coded primary system-organ class (SOC) and preferred term (PT). The summaries will be presented overall (severity grades 1-5) and for grade ≥ 3 events and by treatment discontinuation. These summaries will present the number and percentage of patients reporting an adverse event for each classification level as well as the number of events reported.

Serious adverse events (SAEs) will be tabulated by treatment group.

Laboratory values will be summarized by treatment group over time and overall.

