10.2.5 POOLABILITY AND OTHER ANALYSES

The number of randomized patients, the number of patients treated, the number of patients in each analysis population will be summarized. The number of patients discontinuing from active treatments and reasons for discontinuation will be summarized. In the same manner the number of patients discontinuing follow up and reasons for discontinuations will be reported.

Listings of reasons for discontinuation from active treatments, from follow up, and reasons efficacy data cannot be evaluated in the PP population will be also provided.

Duration of follow up will be described by descriptive statistics such as median and interquartile range.

Demographic, patient and disease characteristics will be listed and summarized using appropriate descriptive statistics.

Multivariate Cox regression analysis of time-to-event efficacy endpoints will be conducted on stratification criteria and other factors such as age, gender, duration of disease prior to randomization to determine the impact of these factors on study endpoints.

As a sensitivity analysis, to address the poolability of data across regions, study sites and gender, a Cox regression analysis of the primary efficacy endpoint, OS, will be conducted with factors of region, study site and gender, and to determine the impact of these factors on OS. Note: region and study site will not be included simultaneously in the model due to collinearity.

Should the impact of region, site or gender on OS be statistically and clinically relevant, the reasons for the observed differential treatment effect, such as patient demographic or clinical characteristics, will be investigated and reported. If the poolability of OS results are in direct question as a result of this sensitivity analysis, the primary endpoint (OS) will also be analyzed separately by region, site or gender. In addition, the primary endpoint (OS) will be analyzed separately by US and non-US region. The specific

mechanism of merging low enrolling study sites into virtual sites for purposes of analysis will be detailed in the Statistical Analysis Plan.

An exploratory analysis will be performed to compare the tumor response rate, based on mRECIST criteria²⁰ and on a blinded centralized independent imaging assessment, between treatment arms using the continuity adjusted Newcombe-Wilson test.

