6.5 Safety Assessments

6.5.1 *Extent of Exposure and Compliance to Study Treatment*

6.5.1.1 *Extent of Exposure to TheraSphere*

TheraSphere exposure will be presented as described below for the Treatment arm. This includes summaries presented separately for TheraSphere administered prior to progression (i.e. prior to date of progression) and post progression (i.e. on or after date of progression) as assessed by investigator according to RECIST 1.1.

- Number of patients who received TheraSphere during the study
- Number of patients who received TheraSphere prior to progression and post progression
- Reasons for not receiving TheraSphere prior to progression
- Reasons for not receiving a second TheraSphere administration prior to progression for patients with bilobar disease
 - Note that bilobar disease is from the stratification factor on the Randomization eCRF page, with any incorrect values at randomization replaced with the corrected value from the eCRF, or values from eCRF for patients enrolled after the changes in stratification factor; this rule also applies to the derivation of unilobar or bilobar disease in later bullets
- Number of patients with bilobar disease at baseline who received TheraSphere prior to progression
 - to both lobes or to the whole liver (i.e. TheraSphere administered to both lobes in a non-lobar approach, for example through the common hepatic artery) on the same day,
 - to both lobes on different days,
 - to both lobes ≥ 28 days apart
 - to both lobes < 28 days apart
 - to one lobe
- Number of patients with unilobar disease at baseline who received TheraSphere prior to progression
 - to both lobes or to the whole liver on the same day,
 - to both lobes on different days,
 - to both lobes ≥ 28 days apart
 - to both lobes < 28 days apart
 - to one lobe
- Number of patients who received first TheraSphere administration post progression

- Patients with at least one TheraSphere administration not completed as planned prior to progression and separately post progression
- Time to the first angiogram (days) prior to progression, defined as (first angiography date prior to progression – randomization date + 1)
- Time to the first TheraSphere treatment (days) prior to progression, defined as (treatment date of first TheraSphere administration prior to progression - randomization date + 1)
- TheraSphere dose absorbed by perfused volume prior to progression and post progression

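### The SAP's only summary of treatment-ending adverse events counts stops of sorafenib alone, which is the whole control regimen but only the last part of the TheraSphere regimen

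*SAP*

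**What the plan says.** Item 11 of the thirteen AE summaries in SAP 8.7.2 is "All TEAEs leading to sorafenib discontinuation". The matching by-patient listing covers "AEs leading to discontinuation of sorafenib". No other AE summary or listing there concerns the ending of treatment.

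Protocol 10.2.4 is wider. It presents TEAEs overall and "for grade ≥ 3 events and by treatment discontinuation", without naming a component. Protocol 10.2.5 adds: "The number of patients discontinuing from active treatments and reasons for discontinuation will be summarized". SAP 8.1 summarizes discontinuation from the study, not from treatment.

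Other provisions that matter here:

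- **Order of treatment.** In the TheraSphere arm, "SOC sorafenib treatment will be initiated at least two (2) weeks after the administration of TheraSphere is completed" (Protocol 9.2.15.1). Patients with bilobar disease are planned to have a second TheraSphere treatment first.
- **Safety groups (SAP 8.3.2).** Patients are analysed by the treatment received before progression. Those who had TheraSphere but no sorafenib form a group of their own.
- **TEAE clock (SAP 6.5.2).** It starts at the first angiogram or the start of sorafenib, whichever is earlier.
- **Event rate (SAP 8.7.2).** For each TEAE category, patients with an event are divided by the total time at risk for TEAEs.
- **Exposure summaries (SAP 6.5.1.1 and 6.5.1.2).** These include "Reasons for not receiving TheraSphere prior to progression", reasons for no second TheraSphere in bilobar disease, administrations not completed as planned, and reasons for not receiving sorafenib.
- **Declared changes (SAP 5.2).** The visible text records changes to the per-protocol and safety populations and to the TEAE definition, but not this one. Section 5.2.4 has no visible text.

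**The concern.** In control, sorafenib is the entire study regimen, so item 11 catches every TEAE that ends study treatment once it has begun. In the TheraSphere arm it catches only those that end the last component. Toxicity that cancels a second-lobe treatment, or after which sorafenib is never begun, falls outside it.

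Item 11 is the one AE table a reader would use to judge how often toxicity ended treatment. Descriptive discontinuation figures are read as evidence on tolerability even when no test is done. As specified, no table tells that reader which AEs, at what grade, kept TheraSphere patients from the rest of their planned regimen.

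**Working it through.** The plan states no AE counts, so there is no figure to reproduce. The check has three parts.

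**1. Where each kind of event lands**

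| Effect of the TEAE | Safety group | In item 11? | Where else the case shows |
|---|---|---|---|
| Stops sorafenib, control | Sorafenib only | Yes | – |
| Stops sorafenib, TheraSphere arm | TheraSphere + sorafenib | Yes | – |
| Cancels or cuts short a second TheraSphere; sorafenib taken later | TheraSphere + sorafenib | No | Reasons for no second treatment; not completed as planned |
| After TheraSphere, sorafenib never started | TheraSphere only | No; zero by construction | Reasons for not receiving sorafenib |
| Cancels the first TheraSphere; sorafenib taken | Sorafenib only | No | Reasons for not receiving TheraSphere |

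The last column refers to exposure summaries. As specified they give a reason, not an AE preferred term or grade.

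**2. Direction of the percentage**

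Let a be the number in the TheraSphere + sorafenib group and d those among them whose sorafenib was stopped for a TEAE. Let m be others in that group whose second TheraSphere was cancelled by a TEAE. Let b be the number in the TheraSphere-only group and k those among them kept off sorafenib by a TEAE.

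- Tabulated share: d/a.
- Any-component share among all TheraSphere-treated patients: (d + m + k)/(a + b).

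With b = k = 0, (d + m)/a is never below d/a, so leaving out m can only lower the TheraSphere + sorafenib figure. With m = 0, (d + k)/(a + b) exceeds d/a only if k/b exceeds d/a. That depends on how many never-starters were kept off sorafenib by an AE rather than by something else.

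Illustration, all inputs assumed: a + b = 230; b = 12, 35 or 58; d/a = 15% or 30%; m/a = 0 or 5%; k/b = 0 to 75%.

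- Lowest: b = 58, a = 172, d = 0.30 × 172 = 51.6, m = k = 0. Then 51.6/230 = 22.4% against 30%, or −7.6 points.
- Highest: b = 58, a = 172, d = 0.15 × 172 = 25.8, m = 0.05 × 172 = 8.6, k = 0.75 × 58 = 43.5. Then 77.9/230 = 33.9% against 15%, or +18.9 points.
- Sign change at b = 35, a = 195, m = 0, k = 0.25 × 35 = 8.75. With d/a = 15%, (29.25 + 8.75)/230 = 16.5%, or +1.5. With d/a = 30%, (58.5 + 8.75)/230 = 29.2%, or −0.8.

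**3. Direction of the event rate**

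The SAP does not define time at risk separately, so I take it as the TEAE window: from the start of treatment to 30 days after the last study treatment. In the TheraSphere + sorafenib group this includes a lead-in of L weeks during which sorafenib cannot be stopped. With s weeks on sorafenib and the same hazard of stopping in both groups, the rate relative to control is

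(s + 30/7) / (L + s + 30/7).

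L runs from 2 weeks (the shortest planned gap, with angiogram and TheraSphere close together) to 14 weeks (second treatment at week 8 plus 6 weeks). I assume s = 12 to 30 weeks.

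- L = 14, s = 12: 16.29/30.29 = 0.54.
- L = 6, s = 20: 24.29/30.29 = 0.80.
- L = 2, s = 30: 34.29/36.29 = 0.94.

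The rate is lowered at every setting tried.

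**The case against.** The strongest reply is that nothing is hidden. Liver events after radioembolization that qualify as TEAEs enter the overall and grade ≥3 tables, and the related, serious or special-interest tables where they apply. SAP 6.5.2 splits Treatment-group TEAEs into those before and after the start of sorafenib. All AEs are listed by patient, laboratory, ALBI and Child-Pugh shifts are shown, and non-receipt reasons are tabulated. This stands, and it limits the point to a missing link between AE and lost treatment.

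The protocol phrase is also undefined. TheraSphere is given in discrete sessions and sorafenib continuously, so reading discontinuation as sorafenib is defensible. And because SAP 5.2.4 has no visible text, an undeclared change cannot be fully established. Both stand. Neither removes the unequal coverage of the two regimens.

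A reader might infer that the table as a whole favours TheraSphere. Suppose 20 of 100 randomized patients per arm have a treatment-ending TEAE, and in the TheraSphere arm 2, 5 or 10 of these fall before sorafenib. The inferred comparison is 20% against 18%, 15% or 10%. The documents do not support this. The table is as treated, so never-starters leave the column. If all the early cases are never-starters it reads 18/98 = 18.4%, 15/95 = 15.8% or 10/90 = 11.1%. The gap that remains comes only from assuming equal totals in both arms. If patients who start sorafenib stop it for AEs equally often, item 11 reads equal.

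Finally, replacing item 11 with a composite that includes non-start would create a new asymmetry. Control patients who never start sorafenib have no TEAE clock and are outside the safety population. That objection is sound and shapes the fix.

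**Conclusion.** The point holds as a reporting gap. Item 11 and its listing are narrower than Protocol 10.2.4, the visible SAP text does not say so, and the narrowing covers all of one regimen and part of the other.

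Two effects point towards TheraSphere: the omission of AEs that cancel a second treatment in patients who later take sorafenib, and the event-rate denominator (0.54 to 0.94 of control at equal hazards, for the assumed durations). For patients who never start sorafenib the sign is unknown, and the overall difference of −7.6 to +18.9 points rests entirely on assumed counts. A general bias in favour of TheraSphere is not shown.

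No endpoint, alpha level or stopping rule is affected, and SAP 8.7.2 plans no inference on AEs. What is at stake is the tolerability reading.

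**What to change.** - Keep item 11. Add separate rows, and a listing, for TEAEs leading to planned TheraSphere not given or not completed, and TEAEs leading to sorafenib never started. Add an any-component row.
- Show these by randomized arm as well as by treatment received.
- Derive them from the action-taken field recorded for each AE (Protocol 12.2) and the non-receipt reasons in SAP 6.5.1.1 and 6.5.1.2, so far as these identify the component. The documents do not show whether action taken is recorded separately for TheraSphere, or whether a non-receipt reason links to an AE record. Check this first and state any limit in the table.
- Footnote that control patients who never start sorafenib have no TEAE clock and are outside the safety population, so the non-start row is not a like-for-like comparison.
- For the sorafenib-discontinuation event rate, count time at risk from the start of sorafenib.
- Record the departure from Protocol 10.2.4 in SAP 5.2.

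The cost is SAP wording and a little more programming, with no change to trial conduct. The reported figure for the TheraSphere arm may rise.

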Treatment Group (TheraSphere followed by Sorafenib)	
As soon as possible after randomization, hepatic angiography will be performed to assess hepatic vascular anatomy and tumor hypervascularity, followed by a ^{99m}Tc-MAA scan to rule-out gastrointestinal flow or unacceptable lung shunting. Embolization may be performed, if necessary, to close off gastrointestinal flow so that the patient can qualify for treatment with TheraSphere. The lobe with the highest tumor burden should be scheduled for first treatment with TheraSphere.
 
Patients will not be able to receive TheraSphere if the potential radiation dose to the lungs exceeds 30 Gy for a single treatment or cumulative 50 Gy or embolization cannot be performed to effectively block GI blood flow from the hepatic arterial system. If radiation exposure to the lungs exceeds 30 Gy (or 50 Gy cumulative), dose reduction of TheraSphere is permitted (minimum dose allowed is 90 Gy ± 10%).
 
If after consideration of dose reduction, radiation exposure to the lung continues to be greater than 30 Gy (or 50 Gy cumulative), sorafenib treatment will be initiated as soon as possible and ^{99m}Tc-MAA will be repeated after 4 weeks of continuous treatment with sorafenib. If radiation exposure to the lung is less than 30Gy for a single treatment or 50Gy cumulative within a target dose of 90-120 Gy +10% , the patient may commence treatment with TheraSphere. In such instances, sorafenib should be discontinued at least 7 days prior to the administration of TheraSphere and resume sorafenib at least 2 weeks after the administration of TheraSphere. If radiation exposure to the lung is outside of the permitted range, treatment with sorafenib should be continued.
 
In the case where TheraSphere could not be delivered at target dose of 120 Gy ± 10% within 28 days of randomization, these patients will be included in the Treatment Group Intent-to-Treat analysis, but not in the Treatment Group Per-Protocol analysis.
 
TheraSphere Treatment #1: TheraSphere treatment should occur within 28 days of randomization, and prior to the initiation of sorafenib. The number of infusions required to achieve lobar treatment will be determined by the Investigator, based on the hepatic vascular anatomy.
 
Patients will receive 120 Gy ± 10% of TheraSphere to the treated lobe of the liver and may be administered in multiple infusions to address vascular abnormalities.
 
TheraSphere Treatment #2: Patients who have bilobar disease at randomization should have TheraSphere administered to the untreated lobe. If needed, a second angiogram and/or ^{99m}Tc-MAA scan should be performed. Such treatments typically take place 28 days after the treatment to the first lobe.
 
From 2 to 6 weeks following TheraSphere treatment of all treatable liver tumors observed at the time of randomization, patients should initiate standard-of-care sorafenib treatment in accordance with the sorafenib label directions.
 
Re-treatment of the same patient with further cycles of TheraSphere is permitted if a

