6.5.2 Adverse Events

All adverse events (AEs) will be documented from the date of randomization until study exit. For patients who permanently discontinue sorafenib in either arm of the study, AEs will be documented for 30 days from the date of discontinuation. After this period, only AEs considered to be related to TheraSphere will be collected.

A treatment emergent AE (TEAE) is defined as an event that was not present at baseline or worsened in severity following the start of treatment through to 30 days after the end of the last study treatment (sorafenib and/or TheraSphere) initiated prior to progression

date by investigator assessment, or start date of subsequent HCC therapy, whichever comes first.

The start of treatment will be defined as the start date of sorafenib and the date of first angiogram, prior to progression date by investigator assessment, whichever occurs first. The last study treatment will be sorafenib for patients who received only sorafenib or both sorafenib and TheraSphere prior to progression, and will be TheraSphere for patients who only received TheraSphere prior to progression. Partial AE start and stop dates will be imputed as described in Section 6.2.1.3.

The investigator's verbatim term of an AE will be mapped to a system organ class and preferred term using the MedDRA Version 14.0 dictionary (Medical Dictionary for Regulatory Activities). The investigator will use the NCI Common Toxicity Criteria for Adverse Events [CTCAE] (version 4.0) or the protocol specific criteria when no NCI CTC criteria are available for the AE to determine the severity of the AE.

Adverse events related to sorafenib, device, and angiographic procedures are defined as those events recorded on the eCRF with relationship of possibly, probably, or definitely relationship. Relation to TheraSphere (device) is not appropriate for the Control group.

The incidence of TEAEs will be the number of patients who had the AE (counted only once) divided by the number of patients in the safety population and represented as a percentage. For subgroup summaries of AEs, the percentage will be represented as the number of patients with the AE event divided by the number of patients of that group in the safety population. The incidence of AEs will be the number of times an event occurs, counting worsening events only once. For worsening events, the AE end date of the earlier AE will be the same as the start date of the same AE with a higher severity.

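### The TEAE 'event rate' in SAP 8.7.2 divides patients with an event by total time at risk, so for common categories it falls as the TEAE window lengthens, whichever group has the longer window

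*SAP*

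**What the plan says.** SAP 8.7.2 lists 13 TEAE summaries. "Patient counts and percentages and event counts will be presented for each treatment group", and a rate "will also be presented by treatment group for each of the above TEAE categories". In the SAP's words, "the event rate is defined as the number of patients with TEAEs in that category divided by the total duration of patients at risk"; the quotient is scaled by 365.25 × 100. The category qualifies the numerator only, and time at risk is not defined further.

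The only TEAE risk period in the SAP is in 6.5.2, with one window per patient. "The start of treatment will be defined as the start date of sorafenib and the date of first angiogram", whichever is earlier. The window runs "following the start of treatment through to 30 days after the end of the last study treatment (sorafenib and/or TheraSphere) initiated prior to progression", or to the start of subsequent HCC therapy if that is sooner. It does not end at a first event.

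The TheraSphere group is to start sorafenib "From 2 to 6 weeks following TheraSphere treatment of all treatable liver tumors observed at the time of randomization" (Protocol 1.0). SAP 8.3.2 groups safety patients by treatment actually received before progression and keeps TheraSphere-only patients as a separate group. SAP 8.7.2 plans no statistical inference on adverse events.

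**The concern.** A rate per patient-year is meant to make groups with unequal observation time comparable. Two standard forms do this under a constant hazard: first events over time to first event, and all events over total time. The SAP takes the numerator of the first and the denominator of the second. Once a patient has had an event in a category, further time adds to the denominator but can add nothing to the numerator. The longer the window, the more such time there is.

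SAP 5.2.6 says the TEAE window was restricted partly to make the groups comparable. A rate that itself depends on window length works against that aim. The categories exposed are the ones most readers look at first: all TEAEs, grade 3 or higher, sorafenib-related, serious, and events of special interest.

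**Working it through.** **Stated figure.** The documents give no adverse event rate, expected rate or mean window, so there is nothing to reproduce. The unit factor is right: 1 patient with an event over 36,525 patient-days gives 1/36,525 × 365.25 × 100 = 1.0 per 100 patient-years.

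**Inputs from the SAP.** The numerator is patients with at least one TEAE in the category. It is "divided by the total duration of patients at risk for TEAEs" (8.7.2), with one window per patient (6.5.2).

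**Assumptions, not in the documents.** The first-event hazard is constant and equal in both groups, and the window lengths are as shown.

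**Formula.** With hazard L per year and a fixed window of T years, the expected SAP rate is 100 × (1 − exp(−L·T))/T, which falls as T rises. For L = 3 (a true rate of 300 per 100 patient-years):
- T = 4/12: 100 × (1 − exp(−1)) × 3 = 189.6
- T = 6/12: 100 × (1 − exp(−1.5)) × 2 = 155.4
- Ratio: 155.4/189.6 = 0.82

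| True rate per 100 patient-years | SAP rate, 4 months | SAP rate, 6 months | Ratio, 6 v 4 |
|---|---|---|---|
| 5 | 5.0 | 4.9 | 0.996 |
| 20 | 19.3 | 19.0 | 0.984 |
| 100 | 85.0 | 78.7 | 0.925 |
| 300 | 189.6 | 155.4 | 0.819 |
| 600 | 259.4 | 190.0 | 0.733 |

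**Second pair of windows, 6 v 8 months.** With hazard h per month the ratio is [(1 − exp(−8h))/8] / [(1 − exp(−6h))/6]. At h = 0.25, 0.5 and 1.0 (300, 600 and 1,200 per 100 patient-years) it is 0.83, 0.77 and 0.75.

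**Variable windows.** With exponentially distributed windows of mean 4 v 6 months (simulated, 400,000 patients per cell), the SAP rates are 18.7 v 18.2 at a true 20 (0.97), 75.0 v 66.8 at a true 100 (0.89) and 150.2 v 120.2 at a true 300 (0.80).

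**The two standard rates in the same simulation, mean windows 4, 6 and 8 months.**
- Time stopped at the first event: 100.0, 100.2, 100.0 at a true 100; 299.4, 300.3, 299.9 at a true 300.
- All events over total time: 100.1, 100.1, 100.4 and 299.8, 300.0, 300.1.

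Neither depends on window length when the hazard is constant.

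**Categories that behave differently.**
- Fatal TEAEs: death ends the time at risk, so there is no artefact (20.0, 20.1, 20.0 at a true 20).
- TEAEs leading to sorafenib discontinuation: with 30 days added to every window, the rate rises slightly with window length (75.0, 80.6, 82.9 at a true 100).
- Device-related TEAEs: SAP 6.5.2 treats device relation as not applicable to the Control group, so there is no arm comparison to distort.

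**Early-onset hazard.** With the hazard assumed threefold in the first month, from a base of 100 per 100 patient-years, and fixed windows of 4, 6 and 8 months, the first-event rate is 159.9, 143.6 and 134.9. The SAP rate is 117.9, 97.4 and 84.7.

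**The case against.** The strongest reply is that little hangs on this rate. No test, boundary or stopping rule uses it. Patient percentages and event counts sit beside it, and percentages move the other way, rising with a longer window. A reader can recover total time from patients and rate, and from that the all-events rate. SAP 6.5.2 also splits Treatment group TEAEs into those before and after the start of sorafenib. All of this stands and limits the consequence. It does not supply the first-event rate, which needs each patient's time to first event and cannot be recovered from the table.

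A second reply is that time at risk could be programmed to stop at the first event in each category. The artefact would then vanish under a constant hazard. The text does not say this, and the one TEAE window it defines does not work that way.

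A reader might infer that the formula makes TheraSphere look safer, because that group's clock starts at the angiogram and includes a lead-in before sorafenib. The documents do not support this as a conclusion. The lead-in lengthens the window only if time on sorafenib is not correspondingly shorter. If sorafenib stops at a similar time after randomization in both groups, the windows may be close to equal. TheraSphere-only patients, whose window has no sorafenib period, are tabulated separately. A reader might also infer that all 13 summaries are distorted in the same way. The fatal, discontinuation and device-related categories are not, and the angiographic-procedure category has no planned control counterpart.

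**Conclusion.** The point holds as a defect of definition. On its plain wording the rate mixes two measures, and for common, non-terminal categories it depends on how long the TEAE window is. If windows differ by 2 months (4 v 6 or 6 v 8), equal risk would appear as a ratio of about 0.93 at a true 100 per 100 patient-years and 0.73 to 0.83 at 300 to 600. At 20 or below the effect is negligible (0.97 to 1.00).

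These sizes rest on assumed window lengths and a constant, equal hazard. Which group, if either, is favoured cannot be determined from the documents; a longer TheraSphere window is possible, not shown. The consequence is confined to descriptive safety tables. Since those tables are the only planned comparison of adverse events, the definition is worth correcting.

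**What to change.** In SAP 8.7.2:
- Define the incidence rate for each category as patients with a first TEAE in that category divided by the summed time from start of treatment to that first event, censored at the end of the 6.5.2 window for patients without one.
- Report all TEAEs in the category over total TEAE time as a separate rate, and keep the label 'event rate' for that one.
- Show total time at risk per safety group.

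The cost is a short text change plus time-at-risk programming for each category. The first-event rate is not a full cure: where risk is concentrated early, as procedural toxicity may be, it still varies somewhat with window length. The existing split of Treatment group TEAEs before and after sorafenib start should be read alongside it.
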